## 9.4. Antitumor Activity Analysis

All antitumor activity analyses will be performed on the safety set. Participants with inadequate baseline or no follow-up assessments will be considered as non-responders.

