#### **Determination of Overall Response by RECIST Version 1.1**

When both target and non-target lesions are present, individual assessments will be recorded separately. The overall assessment of response will involve all parameters as depicted in Table 5.

Target Lesions	Non-Target Lesions	New Lesions	Overall Response
CR	CR	No	CR
CR	Non-CR/non-PD	No	PR
CR	Not evaluated	No	PR
PR	Non-PD or not all evaluated	No	PR
SD	Non-PD or not all evaluated	No	SD
Not all evaluated	Non-PD	No	NE
PD	Any	Yes or No	PD
Any	PD	Yes or No	PD
Any	Any	Yes	PD

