3.2. Secondary Endpoints

3.2.1. Confirmed Objective Response Rate (ORR)

Objective Response (OR) based on investigator assessment is defined as CR or PR according to RECIST v1.1 from date of first dose until documented PD or start of new anticancer therapy without regard to discontinuation from treatment. Both CR and PR must be confirmed by repeat assessments performed no less than 4 weeks after the criteria for response are first met. Participants without a CR or PR or with death prior to first post-baseline assessment, inadequate baseline assessment, new anticancer therapy started prior to first post-baseline assessment, and all post-baseline disease assessments missing will be considered as non-responders.

ORR is defined as the percent of participants with best overall response (BOR) as confirmed CR or confirmed PR according to RECIST version 1.1 BOR is defined in section 6.2.1.

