5.2.8. Adequate Baseline Tumor Assessment

Adequate baseline is defined using the following criteria:

- All baseline assessments must be within 35 days prior to and including the date of first dose.
- All documented lesions must have non-missing assessments (i.e. non missing measurements for target lesions and non-missing lesions status at baseline for nontarget lesions).
- Measurable disease at baseline (see Section 5.2.5 for the definition of measurable disease)

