6.2. Secondary Endpoints

6.2.1. Confirmed OR

Analysis set: Safety: All enrolled participants who take at least 1 dose of Lorlatinib **Analysis methodology**:

• Objective Response Rate (ORR) defined as the percentage of participants with a confirmed best overall response (BOR) of CR or PR according to RECIST v1.1. BOR will be determined based on reported overall responses at different evaluation timepoints by the investigator from the date of treatment start until documented

disease progression or start of new anticancer therapy, according to the following rules:

- CR = at least two determinations of CR at least 4 weeks apart and documented before progression and start of new anticancer therapy
- PR = at least two determinations of PR or better (and not qualifying for a CR) at least 4 weeks apart and before progression and start of new anticancer
- o SD (for participants with at least one measurable lesion at baseline) = at least one SD assessment (or better and not qualifying for CR or PR) ≥ 6 weeks after date of treatment start and before progression and the start of new anticancer therapy
- Non-CR/Non-PD (for participants with only non-target disease at baseline) = at least one Non-CR/Non-PD assessment (or better and not qualifying for CR ≥ 6 weeks after date of treatment start and before progression and the start of new anticancer therapy
- o PD = progression ≤ 13 weeks after date of treatment start and not qualifying for CR, PR or SD
- O Not Evaluable (NE) = all other cases.

Clinical deterioration will not be considered as documented disease progression.

- participants without documented CR or PR will be considered as non-responders
- 95% CI interval for ORR using the Wilson's Score method

Intercurrent events and missing data:

- data on response after subsequent anticancer therapy is administered will be excluded
- participants with death prior to first post-baseline assessment, inadequate baseline
 assessment, new anticancer therapy started prior to first post-baseline assessment, and
 all post-baseline disease assessments missing will also be considered as nonresponders.

Summaries used for reporting:

- The frequency (number and percentage) of participants with BOR of CR, PR, SD, PD, non-CR/non-PD (applicable only to participants with non-measurable disease at baseline), and NE (not evaluable)
- ORR estimated by dividing the number of participants with OR (CR or PR) by the number of participants in the safety set

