6.5. Baseline and Other Summaries and Analyses

6.5.1. Baseline Summaries

• Demographic and Physical Characteristics

The following demographic and baseline characteristics will be summarized by number and percentage:

- o Gender (male, female)
- o Age (18-<45; 45- <65; >65)
- ECOG Performance status

Age (continuous) and weight (kg) will be summarized with descriptive statistics (mean, median, Std Dev, minimum, and maximum, inter quartile range).

Disease Characteristics

The following baseline disease characteristics will be summarized by number and percentage:

Measurable disease at baseline (yes/no) (see Section 5.2.5)
 PFIZER CONFIDENTIAL

^a more than 26 weeks after last adequate tumor assessment.

- o Involved tumor sites at baseline.
- O Number of sites of disease at baseline $(1, 2, \ge 3)$

Involved tumor sites at baseline will be derived from target and non-target lesions at baseline. Each participant will be counted once per organ. Similarly, number of sites of disease at baseline will be derived by counting the number of unique organ sites from target and non-target lesions at baseline. "Other" will be counted as one organ site.

• Medical History

Medical history will be coded using the most current version of MedDRA and summarized by MedDRA's SOC and PT. Each participant will be counted only once within each PT or SOC. Summaries will be ordered by primary SOC and PT in descending order of frequency. Separate summaries will be provided for past and present conditions.

• Prior Anticancer Treatments

Prior anticancer treatments include systemic therapy, radiation, and surgery. The number and percentage of participants in each of the following anticancer therapy categories will be tabulated:

- o Participants with at least one type of prior anticancer treatment;
- o Participants with at least one prior anticancer drug therapy;
- o Participants with at least one prior anticancer radiotherapy;
- o Participants with at least one prior anticancer surgery.

Prior anticancer drug therapy will be summarized as follows based on the number and percentage of participants:

- o Number of prior anticancer therapy regimens: missing $/1/2/3/\ge 4$;
- o Number of participants who received prior chemotherapy
- Number of participants who received 1st generation (Crizotinib) or 2nd generation (Alectinib, Certinib or Brigatinib) ALK Inhibitor (ALKi) as Prior ALKi

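### Measurable disease is part of an adequate baseline in SAP 5.2.8 but not of eligibility or of the best-response rules, so the response table and the ORR numerator can disagree, and the CNS measurability wording does not match Protocol 7.1 (minor)

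*SAP*

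**What the plan says.** **Baseline rule.** SAP 5.2.8 sets three conditions for an adequate baseline tumor assessment. The third is "Measurable disease at baseline (see Section 5.2.5 for the definition of measurable disease".

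**Consequence.** Protocol 9.4: "Participants with inadequate baseline or no follow-up assessments will be considered as non-responders". SAP 3.2.1 has the same rule in a longer list: "inadequate baseline assessment, new anticancer therapy started prior to first post-baseline assessment, and all post-baseline disease assessments missing will be considered as non-responders". SAP 6.2.1 repeats it, and SAP 3.2.2 repeats it for the intracranial endpoint.

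**Who can be enrolled.** None of the 13 inclusion and 12 exclusion criteria (Protocol 4.1 and 4.2) requires measurable disease. SAP 6.5.1 plans a baseline row "Measurable disease at baseline (yes/no", so the plan provides for participants without it.

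**Best overall response.** The CR rule in SAP 6.2.1 is "CR = at least two determinations of CR at least 4 weeks apart and documented before progression and start of new anticancer therapy". It carries no condition on the baseline. Participants with only non-target disease get their own category, defined by "at least one Non-CR/Non-PD assessment (or better and not qualifying for CR", and their own row in the BOR table.

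**ORR.** SAP 3.2.1 defines ORR through BOR. SAP 6.2.1 gives the calculation: "ORR estimated by dividing the number of participants with OR (CR or PR) by the number of participants in the safety set".

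**CNS lesions.** The CNS bullet of SAP 5.2.5 accepts lesions of 5 mm or more on contrast MRI acquired with 1 mm slices. Protocol 7.1 specifies 1 mm slices for CNS lesions of 5 to 10 mm and 5 mm slices for those above 10 mm.

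**The concern.** Two rules bear on the same participant and point in opposite directions. The BOR rules are written so that someone with only non-target disease can be a CR. The baseline rule makes the same person a non-responder because there is no measurable lesion. The SAP does not say how the BOR table should show such a case.

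At stake are the agreement between the BOR table and ORR, and membership of the DoR set, which SAP 6.2.3 limits to participants with a confirmed objective response. If the point is left open, it will be settled in programming, in an open-label study with investigator-assessed response.

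The CNS wording is a second route to the same result. A participant imaged as the protocol specifies can fail the SAP definition of measurable disease, and then a confirmed PR is scored as a failure.

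**Working it through.** **1. The plan's own figure.** The only design figure is the maximum standard error of 0.05 for an AE rate with 100 participants (Protocol 9.2). It reproduces: √(0.5 × 0.5 / 100) = 0.05. The point made here does not depend on it.

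**2. Participant A: only non-target disease, two CR assessments four weeks or more apart.**

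| Rule | Result |
|---|---|
| Protocol 4.1 and 4.2 | eligible |
| SAP 6.2.1, CR rule | BOR = CR |
| SAP 5.2.5 and 5.2.8 | no measurable disease, so baseline inadequate |
| SAP 3.2.1, SAP 6.2.1, Protocol 9.4 | non-responder for ORR |
| SAP 6.2.3 | not in the DoR set, if the non-responder rule prevails |

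The not-evaluable category does not remove the conflict. It takes whatever the earlier rules leave over, and A has already met the CR rule. Nothing in 6.2.1 assigns it for an inadequate baseline. Protocol Appendix 3, Table 5 does not help either, because it is introduced for a different case: "When both target and non-target lesions are present, individual assessments will be recorded separately".

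**3. Participant B: the only target lesions are CNS lesions over 10 mm, imaged on 5 mm slices as in Protocol 7.1, with a confirmed PR.** The other bullets of SAP 5.2.5 concern CT, caliper measurement and nodes on CT. The CNS bullet needs 1 mm slices. Read literally, B has no measurable disease, so the baseline is inadequate and B is a non-responder, although BOR by 6.2.1 is PR.

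**4. Size per case.** Change in ORR = 1/N. With N = 100 treated that is 1 point. For IC-ORR the denominator is participants with CNS metastases, a number the documents do not give. If it were 20 to 40 (assumed), one case would move IC-ORR by 1/20 = 5 points down to 1/40 = 2.5 points.

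**5. How often, for participants like A.** Let m be the share without measurable disease and c their confirmed-CR rate. Both are assumptions. Expected ORR loss = 100·m·c points. Chance of at least one case among 100 = 1 − (1 − m·c)^100.

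| m | c | Expected loss (points) | Chance of at least one case |
|---|---|---|---|
| 5% | 2% | 0.1 | 10% |
| 5% | 5% | 0.25 | 22% |
| 10% | 10% | 1.0 | 63% |

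If m or c is zero, both results are zero.

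**6. Against sampling error.** The protocol cites a 32% response rate (9/28) in the cohort pretreated with a second-generation inhibitor. At that rate, one case takes ORR from 32/100 (Wilson 95% CI 23.7 to 41.7) to 31/100 (22.8 to 40.6). The standard error at 32% is √(0.32 × 0.68 / 100) = 4.7 points. One case also removes 1/32 = 3.1% of the DoR set.

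The documents give no basis for estimating how many participants resemble B.

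**The case against.** The strongest reply is that ORR is not really in doubt. The non-responder rule appears in Protocol 9.4 and in SAP 3.2.1 and 6.2.1, and in 6.2.1 it follows the BOR rules as a further condition. It most naturally prevails, and ORR and the DoR set then follow. A reader might infer that ORR is undefined, or that scoring these participants as failures is an error. The documents support neither. The rule is a conservative choice in a single-arm study, and counting CRs that rest on non-target disease, which Appendix 3 assesses qualitatively, is debatable. What stands is that the BOR table as written does not follow the rule: its non-CR/non-PD row consists of participants whom 5.2.8 calls inadequate.

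The SAP joins its list with *and*, which might suggest that all items must hold together. They cannot sensibly do so, and Protocol 9.4 uses *or*.

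A reader might also infer that SAP 5.2.5 wrongly shuts out nodes and other body lesions measured by MRI, since Protocol 7.1 allows MRI of chest, abdomen and pelvis. That does not hold for nodes: Appendix 3 itself sets a CT criterion for them. Its size list for other body lesions also names CT, besides caliper and chest X-ray. Only its text on bone lesions mentions MRI.

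The CNS slice mismatch is real but narrow for overall ORR, because one qualifying lesion anywhere is enough. For IC-ORR, adequate baseline is defined once and per participant, so the default reading is any lesion. That is a matter for clarification, not a contradiction.

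**Conclusion.** The concern holds in a limited form, and its severity is minor. The SAP has two rules that give different answers for a confirmed CR in a participant with only non-target disease. On the natural reading, what remains is mainly a reporting inconsistency: CR plus PR in the BOR table need not equal the ORR numerator. The CNS wording in SAP 5.2.5 does not match Protocol 7.1 and, taken literally, turns some confirmed PRs into failures.

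Both routes can only lower ORR. Each case is worth 1 point at N = 100, and more for IC-ORR if its denominator is smaller. A one-point shift is well inside the sampling error shown above. The frequency rests wholly on assumed inputs and may be zero, so gaps of several points, which need many such participants with a high CR rate, have no support in the documents. The endpoints affected are secondary and descriptive. The primary AE endpoint is unaffected.

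**What to change.** Change the SAP only, before database release.

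1. **One rule throughout.** Apply the same rule to BOR, ORR, IC-ORR, DoR and IC-DoR so that CR plus PR equals the ORR numerator. The smallest change is to state in 6.2.1 that 5.2.8 governs and how BOR is shown for participants without measurable disease. For example, keep the non-CR/non-PD row and list any confirmed CR among them separately, outside the CR row. If they are all made not evaluable instead, the non-CR/non-PD row would be empty and should go. A supporting summary that counts their confirmed CRs is optional. It would need one line on deriving overall response for non-target-only disease, which Table 5 does not cover.
2. **CNS bullet of 5.2.5.** Accept CNS lesions over 10 mm on the 5 mm MRI slices that Protocol 7.1 specifies.
3. **Clarification in 6.2.2.** State whether adequate baseline for IC-ORR is judged on CNS lesions or on any lesion.

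The cost is a few sentences in SAP 5.2.5, 6.2.1 and 6.2.2, with a cross-reference in 5.2.8. No new data and no change of sample size are needed. Protocol section 9 lets the SAP modify the planned analyses and reserves amendments for major changes to the primary endpoint, so no protocol amendment is needed.

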5.2.9. Adequate Post-baseline Tumor Assessment

An adequate assessment is defined as an assessment where a response of CR, PR, Stable Disease (SD), non-CR/non-PD, or PD has been provided by the investigator. Timepoints where the response is not evaluable, or no assessment was performed will not be used for determining the censoring date.

5.2.10. Nominal and Unscheduled Visits

For all algorithms and analyses, visit labels as specified on the CRF will be used as the nominal timepoint (i.e. assessment will not be slotted).

Unless otherwise specified, unscheduled assessments will not be displayed in summary tables by nominal visit/timepoint. Unscheduled assessments will be used when deriving baseline and worst case on-treatment for adverse events laboratories and vital signs assessments. Additionally, unscheduled tumor assessments will be used for antitumor activity analyses (e.g. defining date of progression/censoring, best overall response, date of last contact).

5.2.11. Standard Derivations and Reporting Conventions

The following conversion factors will be used to convert days into weeks, months or years: 1 week = 7 days, 1 month = 30.4375 days, 1 year = 365.25 days.

Demographics and physical measurements:

• Age [years]:

o (year of given informed consent - year of birth)

For reporting conventions, mean and median should generally be displayed one more decimal place than the raw data and Std Dev should be displayed to two more decimal places than the raw data. Percentages will be reported to one decimal place. The rounding will be performed to closest integer / first decimal using the common mid-point between the two consecutive values. Eg, 5.1 to 5.4 will be rounded to an integer of 5, and 5.5 to 5.9 will be rounded to an integer of 6.

5.2.12. Analyses for Continuous and Qualitative Variables

Continuous variables will be summarized using descriptive statistics ie, number of nonmissing values and number of missing values [ie, n (missing)], mean, median, Std Dev, minimum, maximum, first and third quartile (Q1 and Q3) and inter-quartile range.

Qualitative variables will be summarized by frequency counts and percentages. Unless otherwise specified, the calculation of proportions will include the missing category. Therefore, counts of missing observations will be included in the denominator and presented as a separate category.

In case the analysis refers only to certain visits, percentages will be based on the number of participants with an assessment at that visit, unless otherwise specified.

5.2.13. Analyses for Time-to-Event Endpoints

Time to event endpoints will be summarized using the Kaplan-Meier method and estimated survival curves will be displayed graphically when appropriate. Graphs will describe the number of participants at risk over time. The median, quartiles, and probabilities of an event at particular points in time will be estimated by the Kaplan-Meier method. Confidence intervals for medians and quartiles are based on the Brookmeyer-Crowley method. Summaries of the number and percentages of participants with an event will also be provided on summary tables and figures.

5.3. Methods to Manage Missing Data

Unless otherwise specified, all data will be evaluated as observed, and no imputation method for missing values will be used.

Any imputations will occur at the analysis dataset level. Additionally, in all data listings imputed values will be presented and flagged as imputed.

Missing statistics, e.g. when they cannot be calculated, should be presented as 'ND' for not done, 'NR' for not reached or 'NA' for not applicable. For example, if N=1, the measure of variability cannot be computed and should be presented as 'ND' or 'NA'.

5.3.1. Missing ECG Data

For QTc analyses, no values will be imputed for missing data.

For pre-dose measurements, if one or two of the triplicate measurements for an ECG parameter are missed, the average of the remaining two measurements or the single

measurement can be used in the analyses. If all triplicate measurements are missing at a timepoint for an ECG parameter, no values will be imputed. If the triplicate needs to be repeated because of an artifact, then the repeated triplicate will be reported on an unscheduled CRF page. Based on a review of the data these unscheduled assessments may be used in place of the assessments for pre-dose. Data review and consultation with the study team is required to flag these cases.

5.3.2. Handling of Incomplete or Missing Dates

5.3.2.1. Adverse Events

AE Onset Date:

The following imputation rules apply if the event is unique for a participant or it is the first of a series of similar events; otherwise, the AE Onset Date will not be imputed:

- If the AE Collection Date is not missing, is less than the Date of First Exposure to Treatment, and is less than the AE Stop Date, then AE Onset Date is set to the Date of AE Collection.
- If the Previous Visit Date is greater than the Date of First Exposure to Treatment and less than the AE Stop Date, the AE Onset Date is set to the previous visit date.
- If the Date of First Exposure to Treatment is greater than the previous visit date and less than the AE Stop Date, the AE Onset Date is set to the Date of First Exposure to Treatment.
- Otherwise AE Onset date is set to the AE Stop date.

AE Stop Date:

Ongoing events will have the AE Stop Date set to one of the following values:

- Date of Death, if the participant died and a date of death exists.
- Maximum of (Withdraw date, AE Onset Date, AE Collection Date) if the participant withdrew from the study and a date of withdraw exists.
- Maximum of (AE Onset Date, Subject Summary Collection Date, AE Collection Date) if the Subject Summary CRF page exists but a date of withdraw does not exists.
- Maximum of (Last Treatment Date, AE Onset Date) if no Subject Summary page exits.

Imputation will only occur if event is unique for the participant, or it is the last of a series of similar events; otherwise the Stop Date will not be imputed. Adverse Events are deemed similar if they have the same verbatim term.

Resolved events will have the AE Stop Date set to the maximum of the AE collection date and the AE Onset date.

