# SCHEDULE OF ACTIVITIES

The Schedule of Activities table provides an overview of the protocol visits and procedures. Refer to STUDY PROCEDURES and ASSESSMENTS sections of the protocol for detailed information on each procedure and assessment required for compliance with the protocol.

The Investigator may schedule visits (unplanned visits) in addition to those listed on the Schedule of Activities, in order to conduct evaluations or assessments required to protect the wellbeing of the participant.

Visit Identifier	Screening	Cycle 1 (28 days)	Visit on Day 1 of Every Cycle	End of Treatment	Follow-Up 
Visit Window	≤28 days	Day 1	±2 days	$\pm 7$ days	
Informed consent 	X	2			
Tumor history	Х				
Medical history	Х				
Physical examination and vital signs	Х	Х	Х	Х	
Body weight		Х	Х	Х	
ECOG performance status	Х	Х	Х	Х	
Contraception check  (as appropriate)		Х	Х	X	Х
Laboratory					
Hematology	Х	(X)	Х	Х	
Blood chemistry	Х	(X)	Х	Х	
Lipids	Х	(X)	Х	Х	
Pregnancy test 	Х	Х	Х	Х	Х
Cardiac Monitoring					
12-Lead ECG 	Х	(X)	X (every cycle up to Cycle 5)	Х	
Treatment					
Lorlatinib			Orally once daily, conti	nuously	
Tumor Assessments					
CT or MRI imaging 	Х		X (every 12 weeks $\pm 1$ week)	Х	
Other Clinical Assessmen					
Serious and non-serious AEs 	Х	Х	Х	X	Х
Concomitant medications and non-drug supportive interventions 	Х	Х	Х	Х	Х

(X): No need to repeat if assessment performed within 7 days prior to Cycle 1 Day 1.

Abbreviations: AE=adverse event; CAP=chest abdomen pelvis; CRF=case report form; CT=computed tomography; CTCAE=Common Terminology Criteria for Adverse Events; ECG=electrocardiogram; ECOG=Eastern Cooperative Oncology Group; MRI=magnetic resonance imaging; NCI=National Cancer Institute; QTc=QT interval corrected for heart rate; RECIST=Response Evaluation Criteria in Solid Tumor; SAE=serious adverse event.

- 1. Informed consent must be obtained prior to undergoing any study-specific procedures that are not considered standard of care.
- 2. Contraceptive check: participant may be contacted by phone to confirm contraception is still appropriate per the protocol.

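### A missing AE onset is set to the AE stop date when the previous visit falls on the first-dose day, which can date the event after it was recorded and sometimes drop it from the TEAE summaries

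*SAP*

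**What the plan says.** SAP 5.3.2.1 gives four onset rules, taken in order. Their scope is limited: "The following imputation rules apply if the event is unique for a participant or it is the first of a series of similar events".

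- Rule 1 handles AEs collected before treatment: "If the AE Collection Date is not missing, is less than the Date of First Exposure to Treatment", and also before the stop date, onset is the collection date.
- Rule 2: "If the Previous Visit Date is greater than the Date of First Exposure to Treatment and less than the AE Stop Date", onset is the previous visit.
- Rule 3: "If the Date of First Exposure to Treatment is greater than the previous visit date and less than the AE Stop Date", onset is the first-dose date.
- Rule 4: "Otherwise AE Onset date is set to the AE Stop date".

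The same section imputes stop dates. Three of the four rules for ongoing events use the onset date, for example "Maximum of (Last Treatment Date, AE Onset Date) if no Subject Summary page exits". So does the rule for resolved events: "Resolved events will have the AE Stop Date set to the maximum of the AE collection date and the AE Onset date". No order between the two imputations is given.

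The protocol's Schedule of Activities has a Cycle 1 Day 1 visit and then a "Visit on Day 1 of Every Cycle", and its AE footnote has AEs recorded at each visit. SAP 5.2.2 starts each cycle on the first non-zero dosing date for that cycle's visit. SAP 3.5.1 counts AEs on the first-dose day as on-treatment. SAP 2.1.1 and 6.1.1.1 exclude from the summaries anything beyond 35 days after last dose or from the start of new anticancer therapy; such data are only listed.

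**The concern.** Rules 2 and 3 both use strict inequalities, so neither applies when the previous visit and first dose share a date. That is the expected situation for any AE first collected at Cycle 2 Day 1, because the visit before it is Cycle 1 Day 1, when dosing normally starts. Had the previous visit been one day earlier, rule 3 would have returned the first-dose date. With equality, onset jumps to the other end of the event.

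Two things follow. The imputed onset can be impossible, because an AE still present when recorded at Cycle 2 Day 1 and resolved later is dated after it was recorded. And if the stop date lies outside the on-treatment window, an event recorded during treatment is no longer treatment-emergent. AE incidence is the primary endpoint of this safety study, and any such error removes on-treatment events.

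**Working it through.** **The plan's own figure.** Protocol 9.2 gives a maximum standard error of 0.05 with 100 participants: sqrt(0.5 × 0.5 / 100) = 0.05. It reproduces and is not in dispute; it serves below as a scale.

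**Inputs.** The four onset rules as listed. Window end = last dose + 35 days, or the day before new anticancer therapy if earlier (SAP 2.1.1). Illustrative study days, chosen here and not taken from the documents: first dose = previous visit = day 1; AE collected on day 29 (Cycle 2 Day 1); onset missing.

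**Applying the rules.** Rule 1 fails, since 29 is not less than 1. Rule 2 fails, since 1 is not greater than 1. Rule 3 fails for the same reason. Rule 4 applies, so onset = stop date in every row. The ongoing rows assume that the stop date is imputed first.

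| Case | Stop date | Window end | Imputed onset | Onset minus collection day | In TEAE summaries |
|---|---|---|---|---|---|
| A. Resolved, last dose day 300 | 20 | 335 | 20 | before collection | yes |
| B. Resolved, last dose day 60, no new therapy | 90 | 95 | 90 | 90 − 29 = 61 | yes |
| C. As B, new therapy day 70 | 90 | 69 | 90 | 61 | no |
| D. Resolved, last dose day 60 | 120 | 95 | 120 | 91 | no |
| E. Ongoing, last dose day 60, withdrawal day 150 | max(150, 29) = 150 | 95 | 150 | 121 | no |
| F. Ongoing, last dose day 60, death day 200 | 200 | 95 | 200 | 171 | no |
| G. Ongoing, last dose day 300, no Subject Summary page | 300 | 335 | 300 | 271 | yes |

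Control: case E with the previous visit before first dose. Rule 3 applies, onset is day 1, and the event is a TEAE. Only the tie between the two dates changes the answer.

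**Smallest distortion.** With the ±2 day visit window, Cycle 2 Day 1 is study day 27 to 31. An AE resolved by then has its onset moved by at most stop day − 1, that is 26 to 30 days, compared with the first-dose date.

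**Order of imputation.** If onset is imputed first in E to G, there is no stop date to compare with or to copy, and onset stays missing. The same happens for a resolved AE with no recorded stop date. Correcting the inequality alone does not repair these cases.

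**After the full fix.** A to G all give onset day 1, and all are TEAEs.

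**Scale.** One participant is 1/100 = 1 percentage point on a preferred term, against a maximum standard error of 5 points. A term going from 6/100 to 5/100 drops out of the table of non-serious TEAEs in more than 5% of participants (SAP 6.1.1.2).

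**The case against.** The strongest reply is that the conditions for losing an event are narrow. Onset must be missing; the event must be unique or first in its series; the previous visit must fall exactly on the first-dose day; and the stop date must lie outside the window. Investigators are responsible for complete records (Protocol 11.1) and sites are monitored (Protocol 10), so missing onsets should be few. Imputed dates are flagged in listings (SAP 5.3), the AE summary tables in SAP 6.1.1 show no onset day or duration, and no hypothesis is tested (SAP 5.1.1). All of this stands, and it limits the severity.

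SAP 3.5 also speaks of safety data collected outside the on-treatment period. An AE recorded at Cycle 2 Day 1 during treatment was collected inside it, so on that wording it might be kept. But SAP 2.1.1, 3.5.1 and 6.1.1.1 define the window by when the event occurs, and that is how a programmer would normally apply an imputed onset. The exclusion is therefore the natural reading, though not the only one.

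A reader might infer that any AE starting in Cycle 1 and resolving after treatment ends is lost. The documents do not support that: case B, resolved within 35 days of last dose without new therapy, stays a TEAE. A reader might also infer that participants who stop very early are the most exposed. The schedule includes an End of Treatment visit, which would normally become the previous visit and fall after first dose, so rule 2 would apply.

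**Conclusion.** The onset rule is wrong as written; the severity is minor. When the previous visit is on the first-dose day, a missing onset is set to the stop date (if one is available), which can be later than the date the AE was recorded. No other section repairs this, since SAP 5.3.2.5 covers only other dates. It also departs from the evident intent of rule 3.

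Loss from the TEAE summaries is conditional: it needs a stop date more than 35 days after last dose, or on or after the start of new anticancer therapy. For ongoing events the result also depends on which date is imputed first, and the SAP does not say.

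The counts at risk are those by preferred term, grade, seriousness and special interest, at 1 percentage point per participant. It would be going too far to conclude that the primary any-AE rate is materially biased, because that indicator changes only for a participant with no other TEAE. The documents give no frequency of missing onsets, so no total can be stated, and the cases above are examples rather than rates.

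The conclusion assumes that the previous visit means the visit before the one at which the AE was collected, and that dosing starts on the Cycle 1 Day 1 visit date. Both are inferred. An unscheduled or End of Treatment visit in between, or a first dose taken on a later day, removes the tie.

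**What to change.** In SAP 5.3.2.1:

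1. Keep rule 1 first, so that an AE collected before first dose keeps its collection date and is not turned into a TEAE.
2. Let rule 3 apply when first dose is on or after the previous visit date, instead of strictly after it.
3. State that onset is imputed before stop date.
4. State that a missing stop date counts as meeting the condition that a date is before the stop date.
5. State that an imputed stop date is never used as the onset.

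For an AE collected on or after first dose with no recorded stop date, onset is then the later of the previous visit and first dose, which agrees with SAP 3.5.1. Items 3 to 5 are needed as well as item 2, because the inequality alone leaves ongoing events unresolved.

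The cost is a few sentences and minor programming, with no change to data collection or dosing. Some imputed onsets move earlier, and some events may return to the TEAE summaries.
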